### 7.3 Prohibited Medications and Treatments

For both the randomized and open-label periods, the following medications are prohibited (for the randomized period, between Visit 1 through Visit 3; for the open-label period, between Visit 3 and Visit 5).

- Investigational therapies
- Chronic inhaled antibiotics other than cycled TISP (e.g., Cayston®, colistin). Chronic treatment is defined as inhaled antibiotics prescribed as a maintenance therapy and not used temporarily to treat a pulmonary exacerbation.
- Increase in chronic systemic corticosteroid dose beyond prednisone equivalent of 10 mg per day, or initiation of chronic systemic (oral or intravenous) corticosteroids at any dose. Chronic use is defined as greater than 10 days continuous use.
- New or increase in ibuprofen dose of greater than 800 mg total dose per 24 hours for more than 5 days
- Nelfinavir, warfarin, haloperidol, or methadone

### 7.4 Change in Medications or Therapies

Subjects should receive all medication as clinically necessary, regardless of what impact this may have on the study.

Maintaining a stable therapeutic regimen between Visit 1 and Visit 5 is desirable to minimize the risk of confounding. Unless otherwise medically indicated, subjects not using these therapies should not be started on them after Visit 1 or at any time during the trial and subjects that have been using them chronically should be strongly encouraged to continue them throughout the entire study period (through Visit 5).

## 8 STUDY TREATMENTS

### 8.1 Randomization

At Visit 1, eligible subjects will be enrolled and randomized to study drug. Study personnel at the investigative site will use the Medidata® Rave and Balance™ systems to randomize each subject. An adaptive randomization (dynamic allocation based on minimization) will be employed. Subjects will be randomly assigned in a 1:1 ratio to azithromycin (500 mg three times per week) or matched placebo. Randomization will be stratified by FEV1 % predicted (25%-50%, >50%-75%, >75%), chronic oral azithromycin use for the past 30 days, inhaled tobramycin formulation (TIS or TIP), and site. The dynamic allocation algorithm seeks to optimize randomization balance by minimizing a weighted average of the marginal imbalance of treatment allocation for each factor and for the study overall. A random element is added to the otherwise deterministic minimization algorithm to reduce allocation predictability by using a biased coin to include a chance of allocation to a treatment arm other than the arm that optimizes balance. After data collection at Visit 1, subjects will be randomized to one of the two treatment groups. To randomize a new subject, study personnel at the investigative site will complete the electronic CRF in the Medidata Rave system required to provide the stratification information and the subject will then be assigned to a treatment group.

## 8.2 Blinding

Study treatment (azithromycin or placebo) will be assigned in a double-blinded fashion. Subjects and site research staff will not know the treatment assigned, with the exception of the dispensing site pharmacist or designee and designated TDNCC personnel.

The following study procedures will be in place to ensure double-blind administration of study treatments:

- Randomization assignments will be stored in a secure database and appropriately protected and backed up
- Access to the randomization code will be strictly controlled and limited to designated TDNCC study personnel
- Test and control treatments will be manufactured to be identical in appearance and taste-matched
- Packaging and labeling of test and control treatments will be identical

The study blind will be broken upon completion of the clinical study and after the study database has been locked and study results released. The site investigators will be provided with each subject's treatment assignment following completion of data analysis.

## 8.3 Unblinding Procedures

During the study, the blind may be broken for individual subjects in emergencies when knowledge of the subject's treatment group is necessary for further patient management or when the event meets the FDA expedited reporting requirements as a suspected adverse reaction that is serious and unexpected (21 CFR 312.32(c)(1)(i)). In those cases, knowledge of the treatment received is necessary for interpreting the event. Individual SAEs that are unexpected, deemed related to study drug, and confirmed by the Medical Monitor will be forwarded to the DSMB Chair within 7 business days. Additional information or data summaries may also be requested by the DSMB at this time.

If the blind is broken and the subject is on study drug, a Safety Report will be sent to all participating investigators. Emergency unblinding procedures are provided in the Study Manual. Refer to protocol section 11.2.1 Serious Adverse Experience Reporting.

## 8.4 Formulation of Test and Control Products

### 8.4.1 Formulation of Test Product

Azithromycin 500 mg capsules will be provided. Over-encapsulated azithromycin tablets capsules will be provided during the randomized period of the study.

During the open-label extension period, commercially-available azithromycin 500 mg capsules (without over-encapsulation) will be used.

### 8.4.2 Formulation of Control Product

Placebo capsules using the same materials used for azithromycin over-encapsulation will be provided. The placebo will be appearance-matched.

### 8.4.3 Packaging and Labeling

Capsules for the randomized period of the study will be provided in labeled bottles. A six-week supply plus one extra (19) of capsules will be included in each bottle. One bottle will be supplied at Visit 1.

If the subject enrolls in the open-label period, commercially-available azithromycin will be provided by the site pharmacy.

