## 4 STUDY DESIGN

### 4.1 Study Overview

This is a prospective, randomized, placebo-controlled, double-blinded study of azithromycin in subjects with chronic *Pa* airway infection using inhaled tobramycin. Subjects who have received two (2) or more cycles of inhaled tobramycin within the 24 weeks prior to enrollment will be recruited into the study. This study will investigate whether azithromycin is associated with poorer clinical and microbiologic outcomes as compared to placebo during concurrent administration of inhaled tobramycin.

[figure not shown]
Approximately 120 eligible subjects will be enrolled and randomized to either azithromycin or placebo at Visit 1, approximately 14 days prior to the start day of their next planned 28-day nebulized solution or dry powder tobramycin (TISP) cycle. Both tobramycin inhalation solution (TIS) and tobramycin inhalation powder (TIP) will be allowed, based on clinical prescription. Tobramycin solution should be nebulized with an approved nebulizer and air compressor.

Subjects will be randomized in a 1:1 fashion to azithromycin (500 mg three times per week) or matched placebo. Randomization will be stratified by FEV1 % predicted (25%-50%, >50%-75%, >75%), chronic oral azithromycin use for the past 30 days, inhaled tobramycin formulation (TIS or TIP), and site. Between Visit 1 (Day -14) and Visit 2 (Day 0), a two-week run-in period will be used to begin administration of either azithromycin or placebo. Among those randomized to azithromycin, the 2-week run-in period will be used to initiate azithromycin and standardize uptake prior to the start of the next TISP cycle. Among those randomized to placebo, the run-in period will be used as a standardized washout prior to the start of the next TISP cycle. Subjects will begin TISP at Visit 2 in addition to their continued dosing of randomized study drug treatment (azithromycin or placebo). Subjects will continue both TISP and study drug dosing for 28 days (up until Visit 3), which corresponds with the end of a clinically prescribed 4-week cycle of TISP.

Subjects completing the study through Visit 3 will be offered participation and consent to an 8-week open-label extension period during which azithromycin will be provided. During the open-label period, subjects will be instructed to remain off of TISP for the first 4-week period, followed by a 4-week period of TISP.

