#### 8.5.1 Dosage/Dosage Regimen

Randomized study drug (azithromycin or placebo) and open-label azithromycin will be taken by mouth three times weekly during the following study periods:

- Treatment V1-V2: azithromycin or placebo without TISP: 14 days
- Treatment V2-V3: azithromycin or placebo with TISP: 28 days

Subjects participating in the optional open-label extension:

- Treatment V3-V4: azithromycin without TISP: 28 days
- Treatment V4-V5: azithromycin with TISP 28 days

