#### 8.5.3 Administration Instructions

Study drug (azithromycin or placebo and open-label azithromycin) should be taken by mouth with food and pancreatic enzymes (if clinically prescribed).

It is recommended that the first dose be taken at the Visit 1 to ensure that the subject is able to swallow the capsule.

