### **10.2 Visit 2 - Day 0 (visit window -2/+4 days)**

1. Administer PRO questionnaires (CFRSD-CRISS and CFQ-R).
2. Review subject diary.
3. Perform pill count on returned study drug.
4. Record any AEs.
5. Record changes to concomitant medications. If a new IV, oral or inhaled antibiotic was prescribed, ensure that a Signs and Symptoms form was completed.
6. Perform an abbreviated physical examination.
7. Measure and record height and weight.
8. Obtain and record vital signs.
9. Perform and record spirometry.
10. If able to expectorate sputum, collect expectorated sputum.
11. Provide subject diary.
12. Review inhaled tobramycin schedule and remind subject to take TISP between Visits 2 and 3.
13. Instruct subject to bring study drug bottle, any remaining capsules, and diary to Visit 3.
14. Schedule subject for Visit 3. Visit 3 should coincide with completion of approximately 4 weeks use of inhaled tobramycin combined with study drug.

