### **End of Randomized Period and Start of Open-Label Period**

### **10.3 Visit 3 – Day 28 (visit window -2/+4 days), Week 4**

1. Administer PRO questionnaires (CFRSD-CRISS and CFQ-R).
2. Review subject diary.
3. Perform pill count on returned study drug.

4. Record TISP use.
5. Record any AEs.
6. Record changes to concomitant medications. If a new IV, oral or inhaled antibiotic was prescribed, ensure that a Signs and Symptoms form was completed.
7. Perform abbreviated physical examination.
8. Measure and record height and weight.
9. Obtain and record vital signs.
10. Perform and record spirometry.
11. Obtain resting ECG.
12. If able to expectorate sputum, collect expectorated sputum.

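### The single 19-capsule bottle can leave a fully adherent participant up to one dose short when Visit 3 falls on Day 31 or 32, and the SAP's fixed 18-dose denominator overstates compliance for the same late visits

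*Protocol*

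**What the plan says.** **Supply.** Protocol 8.4.3: "A six-week supply plus one extra (19) of capsules will be included in each bottle. One bottle will be supplied at Visit 1". The Schedule of Events (Appendix 1) marks dispensing of randomized drug at Visit 1 only. At Visit 2 staff count pills and hand the same bottle on (10.2): "Instruct subject to bring study drug bottle, any remaining capsules, and diary to Visit 3". The further shipments mentioned in 8.5 go to site pharmacies, not to participants.

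**Dosing.** One capsule is taken three times a week. On the start, 8.5.3 says: "It is recommended that the first dose be taken at the Visit 1". On the second interval, 8.5.1 says: "Treatment V2-V3: azithromycin or placebo with TISP: 28 days". Section 4.1 says: "Subjects will continue both TISP and study drug dosing for 28 days (up until Visit 3".

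**Windows.** Visit 1 is Day -14. Section 10.2 is headed "Visit 2 - Day 0 (visit window -2/+4 days", and Visit 3 in 10.3 is at "Day 28 (visit window -2/+4 days), Week 4". Section 10.2 also ties the two visits together: "Visit 3 should coincide with completion of approximately 4 weeks use of inhaled tobramycin combined with study drug". The synopsis instead attaches -2/+4 days to each treatment interval (14 days, then 28 days), although the same entry describes the randomized study as lasting up to 42 days.

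**Compliance.** SAP A.3 divides doses taken by a fixed 18 expected doses. The per-protocol population in SAP 2.4 and A.3 requires at least 80% of doses.

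**The concern.** Supply is sized for 42 days, but a visit schedule that follows every instruction can run a few days longer. A participant whose Visit 2 is held at Day 4 and who then takes 28 days of tobramycin reaches Visit 3 on Day 32. If the bottle is empty by then, a scheduled study-drug dose cannot be taken while tobramycin is still running, immediately before the spirometry that defines the primary endpoint. Active exposure is lost only in the azithromycin arm, so any consequence is a slight dilution of the contrast between arms.

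The same late visit affects the compliance measure. More than 18 doses are due, but the SAP still divides by 18, so a participant can look more compliant than they were.

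**Working it through.** **Inputs.** 19 capsules, one bottle (8.4.3); three doses a week (8.5.2); Visit 1 at Day -14 (10.1); Visit 2 at Day 0, -2/+4 (10.2); Visit 3 at Day 28, -2/+4 (10.3, Appendix 1); 18 expected doses (SAP A.3). Days below use the protocol's numbering; add 14 for days since Visit 1. The Monday/Wednesday/Friday calendar is my assumption, with each weekday tried as the start. A dose counts as due if it falls strictly before the day of Visit 3.

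**1. The plan's own figure.** 6 weeks × 3 + 1 = 19. It reproduces. The open-label supply follows the same rule: 8 × 3 + 1 = 25.

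**2. First dose at Visit 1.**

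| First dose on | 19th capsule | 20th dose due | Short, Visit 3 on Day 30 | Day 31 | Day 32 |
|---|---|---|---|---|---|
| Monday | Day 28 | Day 30 | 0 | 1 | 1 |
| Wednesday | Day 28 | Day 30 | 0 | 1 | 1 |
| Friday | Day 28 | Day 31 | 0 | 0 | 1 |

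At Day 32, 20 doses are due, and 20 − 19 = 1. The last capsule was taken 4 days earlier and the next dose is 1 to 2 days overdue. If a dose due on the visit day itself is counted, the Monday start is 2 short at Day 32 (21 due).

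**3. First dose later.** Starting one day after Visit 1, the shortfall at Day 32 is 1, 1 and 0 across the three patterns. Starting two days after, it is 0 in all three.

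**4. Late Visit 2.** Visit 2 at Day 4 plus 28 days gives Day 32. With the first dose at Visit 1, 8 doses are due before Visit 2, leaving 19 − 8 = 11 capsules. Doses due from Day 4 to Day 31 number 20 − 8 = 12. So 12 − 11 = 1 short in all three patterns. Tobramycin started on Day 4 runs through Day 31, so the missed dose (Day 30 or 31) falls in its last two days.

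**5. How many visit dates are exposed.** Permitted Visit 3 days run from Day 26 to Day 32, which is 7 days. Only Days 31 and 32 are affected.

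**6. Interval reading of the windows.** (14 + 4) + (28 + 4) = 50 days after Visit 1, or Day 36. Doses due: 22 with the first dose at Visit 1 (3 short), 21 with the first dose one or two days later (2 short).

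**7. Effect on the per-protocol set.** Taking all 19 capsules gives 19/20 = 95% of doses due at Day 32, or 19/22 = 86% at Day 36. Both exceed 80%, so the supply gap alone excludes no one.

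**8. The fixed denominator.** With Visit 3 at Day 32 and 20 doses due, 15 doses taken is 15/20 = 75%, but it is scored 15/18 = 83%. Fourteen doses fails either way (14/18 = 78%) and sixteen passes either way (16/20 = 80%), so at Day 32 only a count of exactly 15 changes sides.

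**The case against.** The strongest reply is that supply matches the regimen as stated. Section 8.5.1 prescribes 14 + 28 days with no window, the synopsis speaks of up to 42 days, and the SAP expects 18 doses. If dosing is meant to stop at six weeks, no planned dose is missed. That reading is possible, but 4.1 carries dosing up to Visit 3, and the synopsis entry that says 42 days goes straight on to allow longer intervals. Even on the strict reading, a Day 32 visit would still come 4 days after the last capsule.

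It is also fair to say that the case needs several things together: a visit on the last one or two permitted days, a first dose at Visit 1 (recommended, not required) and near-perfect adherence. Missed, held or twice-weekly doses leave spare capsules. Section 10.2 asks only for approximately four weeks of combined use, and one dose in 12 arguably sits within that. All of this stands and limits the point; it does not remove the mismatch.

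Three stronger readings are tempting and are not supported:

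- *The bottle fails any visit after Day 28.* The 19th capsule falls on Day 28, but the next dose is not due until Day 30 or 31, so visits up to Day 30 are covered.
- *Late participants run 2 to 3 doses short.* That needs the synopsis's interval windows. Sections 10.2 and 10.3 and Appendix 1 attach the windows to nominal days, which caps Visit 3 at Day 32.
- *Compliance can already read 122%.* That is 22/18 and needs 22 capsules. With the present bottle the maximum is 19/18 = 106%.

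**Conclusion.** The mismatch is real but small. On windows fixed to nominal days, a fully adherent participant is short by 0 or 1 dose, and only when Visit 3 falls on Day 31 or 32. This assumes a Monday/Wednesday/Friday calendar, dosing up to the actual Visit 3, and a count of doses due before the visit day.

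A reader might infer that the primary FEV1 comparison is compromised. The documents do not support that. At most one late dose is lost, the affected participants stay in the m-ITT population, and any effect runs toward no difference. It is likely negligible. It cannot be sized, because the documents give neither the share of late visits nor the FEV1 effect of one missed dose.

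The fixed 18-dose denominator is a separate small flaw. It overstates compliance at late visits and can place a 75%-compliant participant above the per-protocol threshold, assuming that threshold uses the A.3 formula, which the SAP implies but does not state. Neither part threatens the trial; both are worth correcting because correction is cheap.

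**What to change.** - **Protocol 8.4.3:** fill each randomized-period bottle with 21 capsules (20 doses due before Day 32 plus one spare). If the sponsor confirms that windows apply to each interval, use 23 (22 plus one spare).
- **Protocol 8.5.1:** state that study drug continues to the actual Visit 3, and say whether the windows are fixed to nominal days or apply to each interval.
- **SAP A.3:** replace the fixed 18 with the doses due from Visit 1 to the actual Visit 3, and say that the per-protocol threshold uses this figure. This should accompany the larger bottle; otherwise a participant who takes all 20 doses would read 20/18 = 111%.

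**Cost.** (21 − 19) × 120 = 240 extra capsules, or (23 − 19) × 120 = 480. These are minimums, because spare bottles stocked across about 40 sites would add to them. The change can apply only to bottles not yet filled. There are also more returned capsules to count and slightly more compliance programming, and the new denominator can move an occasional participant out of the per-protocol set. No visit, eligibility criterion, endpoint or sample size changes.

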### 8.5 Supply of Study Drug to the Site

Study drug for the randomized period will be shipped to each site pharmacy. The initial study drug shipment will be shipped after site approval to enroll (i.e., all required regulatory documentation has been received by the TDNCC and a contract has been executed). Subsequent study drug shipments will be made as needed.

For the open-label period, sites will obtain their own supplies of commercially-available azithromycin capsules.

#### 8.5.1 Dosage/Dosage Regimen

Randomized study drug (azithromycin or placebo) and open-label azithromycin will be taken by mouth three times weekly during the following study periods:

- Treatment V1-V2: azithromycin or placebo without TISP: 14 days
- Treatment V2-V3: azithromycin or placebo with TISP: 28 days

Subjects participating in the optional open-label extension:

- Treatment V3-V4: azithromycin without TISP: 28 days
- Treatment V4-V5: azithromycin with TISP 28 days

#### 8.5.2 Study Drug Preparation and Dispensing

Appropriately trained site personnel will be responsible for dispensing study drug (includes the randomized period and open-label period). Study drug shall be dispensed and labeled in accordance with federal and local state Board of Pharmacy regulations. Capsules will be provided in labeled bottles from the study pharmacy with instructions to take one capsule three times weekly.

If the subject enrolls in the open-label period, an 8-week supply plus one extra (25) of commercially-available azithromycin tablets will be dispensed at Visit 3.

#### 8.5.3 Administration Instructions

Study drug (azithromycin or placebo and open-label azithromycin) should be taken by mouth with food and pancreatic enzymes (if clinically prescribed).

It is recommended that the first dose be taken at the Visit 1 to ensure that the subject is able to swallow the capsule.

#### 8.5.4 Storage

Study drug (azithromycin or placebo and open-label azithromycin) should be stored by the study site at controlled room temperature, 15 to 30 °C (59 to 86 °F) in a secure area under restricted access. If the temperature of study drug storage in the clinic/pharmacy exceeds or falls below this range, this should be reported to the Sponsor or designee.

Subjects will be instructed to store study drug (azithromycin or placebo and open-label azithromycin) in original packaging at room temperature.

### 8.6 Dose Modifications

#### 8.6.1 Due to Toxicity

If a study subject has moderate to severe toxicity (refer to Study Manual), the following schedule for dosage adjustment can be made at the discretion of the site investigator:

- If a study subject receiving study drug three times weekly (TIW) experiences drug-related toxicity, the dosing INTERVAL of the study drug will be extended to two times weekly (BIW; e.g., Monday and Thursday)
- If a study subject does not tolerate receiving study drug BIW, the subject should be permanently discontinued from study drug due to intolerance.

Dose can return to TIW at the discretion of the site investigator.

#### 8.6.2 Due to Treatment with Antibiotics – Temporary Discontinuation of Study Drug

Study drug should be temporarily discontinued for subjects prescribed macrolide antibiotics. Study drug may be temporarily discontinued at the discretion of the treating clinician during acute treatment with other medications (e.g., additional antibiotics or drugs believed to increase QT prolongation).

Regardless of study drug use, subjects should be encouraged to complete all study visits.

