## 7.2 Conditionally Allowed Medications and Treatments

Acute treatment with drugs categorized as known to prolong QT interval is allowed according to the following:

- For drugs commonly used to treat CF patients (e.g. ciprofloxacin, levofloxacin, moxifloxacin, fluconazole, propofol, sevoflurane, ondansetron), study drug (azithromycin or placebo) or open-label azithromycin **does not** need to be stopped.
- For all other drugs categorized as known to prolong QT interval, acute use is allowed but study drug (azithromycin or placebo) or open-label azithromycin **must** be temporarily stopped during use of these medications. After acute treatment is completed, subjects should re-start study drug or open-label azithromycin on the next scheduled treatment day.
- Ongoing chronic treatment (>30 days prior to Visit 1) with antidepressant medications citalopram and escitalopram is allowed without affecting study participation if:
  - The subject has been using both chronic oral azithromycin AND citalopram (or escitalopram) consistently for greater than 30 days at Visit 1 AND
  - The Visit 1 ECG demonstrates QTc within the normal limits as defined by the protocol

Drugs known to prolong QT interval are described as follows: “Substantial evidence supports the conclusion that these drugs prolong the QT interval AND are clearly associated with a risk of torsades de pointes (TdP), even when taken as directed in official labeling”, and listed on the CredibleMeds® Website ([Composite List of All QT Drugs](#) under the category “Known Risk of TdP”).

Acute use of macrolide antibiotics may be required for certain infections and is allowed but also requires temporarily stopping the study drug or open-label azithromycin. The study drug or open-label azithromycin should be restarted on the next scheduled day following completion of the prescribed macrolide antibiotic.

Treatment for pulmonary exacerbations as required for acute care is allowed except for treatments noted in the prohibited medications section below. Physicians are encouraged to prescribe acute antibiotic therapy and initiate or increase the dose of acute systemic corticosteroids (defined as less than 10 days) only in the presence of increased symptoms suggesting a pulmonary exacerbation.

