**9.1.13 Electrocardiogram (ECG)**

Standard 12-lead ECG tracing will be obtained as noted in the Schedule of Events. ECG is only needed for an acute visit if the subject has a cardiovascular-related AE or will no longer be participating in the study.

Testing will be conducted and reviewed at the site by trained personnel with experience interpreting electrocardiograms. Any test results of clinical concern, should be reported to the Medical Monitor to determine follow up actions as described below.

Testing will be performed using an ECG machine that automatically calculates the heart rate and measures PR, QRS, QT, and QTc intervals. All tests will be measured in Lead II.

Abnormal results at the time of follow-up testing are defined as a QTc >500 msec, or an increase in QTc of  $\geq 60$  msec. It is recommended that testing be repeated after 10 minutes for any ECGs that meet the protocol definition for abnormal. If test results are confirmed, subjects will be instructed to stop study drug or open-label azithromycin and the site investigator will continue to observe the subject for clinical signs of arrhythmia (specifically torsades de pointes).

The ECG tracing will be collected for additional safety review.

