## 13 PROTOCOL VIOLATIONS

A protocol violation occurs when the subject, investigator, or the Sponsor fails to adhere to significant protocol requirements affecting the inclusion, exclusion, subject safety and primary endpoint criteria. Protocol violations for this study include, but are not limited to, the following:

- Failure to meet eligibility criteria
- Use of a prohibited concomitant medication. This includes the use of conditionally allowed medications without meeting the criteria to use these medications (e.g. Temporarily stopping study drug or open-label azithromycin).
- Failure to obtain spirometry at Visits 1-3

Failure to comply with Good Clinical Practice (GCP) guidelines will also result in a protocol violation. The Sponsor-Investigator will determine if a protocol violation should result in early discontinuation of study treatment for a subject.

When a protocol violation occurs, it will be discussed with the investigator and a Protocol Violation Form detailing the violation will be generated. This form will be signed by a Sponsor representative and the site investigator. A copy of the form will be filed in the site's regulatory binder and in the Sponsor's files. The site will report the violation to their IRB in accordance with their IRB reporting requirements.

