## 19 APPENDIX 1 SCHEDULE OF EVENTS

	RANDOMIZED, PLACEBO-CONTROLLED, DOUBLE BLIND		OVERLAP	OPEN-LABEL, FOLLOW-ON		UNSCHEDULED/ EARLY TERM VISIT f
	VISIT 1* Day -14	VISIT 2 (Day 0) (-2 to +4 days)	VISIT 3 Day 28 (-2 to +4 days)	VISIT 4 EXT Day 56 (± 4 days)	VISIT 5 EXT Day 84 (±4 days)	
Informed Consent	X		X e			
Respiratory Culture (as needed)	X h					
Demographics and Medical History	X					
Complete CFQ-R and CFRSD-CRISS	X	X	X	X	X	X
Complete Physical Exam	X					X
Abbreviated Physical Exam		X	X	X	X	
Height	X	X	X	X	X	X
Weight	X	X	X	X	X	X
Vital Signs	X	X	X	X	X	X
Spirometry	X	X	X	X	X	X
Pregnancy Test at site (Urine or Serum) a	X					
ECG Testing	X		X		X	X b
Collect sputum for analysis and banking c	X	X	X	X	X	X
Randomize to azithromycin or placebo	X					
Dispense azithromycin/placebo dose and review dose schedule	X					
Dispense open-label azithromycin and review dose schedule			X e			
Provide Subject Diary	X	X	X e	X		

	RANDOMIZED, PLACEBO-CONTROLLED, DOUBLE BLIND		OVERLAP	OPEN-LABEL, FOLLOW-ON		UNSCHEDULED/ EARLY TERM VISIT f
	VISIT 1* Day -14	VISIT 2 (Day 0) (-2 to +4 days)	VISIT 3 Day 28 (-2 to +4 days)	VISIT 4 EXT Day 56 (± 4 days)	VISIT 5 EXT Day 84 (±4 days)	
Instruct to hold use of inhaled tobramycin for off-cycle until the next study visit	X		X e			
Concomitant Medication Review	X	X	X	X	X	X
Adverse Events		X	X	X	X	X
Review Subject Diary and pill count		X	X	X	X	X
Record TISP use			X		X	X
Review inhaled tobramycin schedule		X		X		
Assess eligibility for Open-label			X e			
Signs and Symptoms Assessment g	Start	➔	Stop Start e	➔	Stop	

\* If the patient does not have sufficient culture history to assess eligibility, a respiratory culture may be collected prior to randomization. If the respiratory culture is positive, the remaining Visit 1 procedures and randomization will be conducted at a subsequent visit.

a Only females of child-bearing potential

b ECG is only required at an Unscheduled visit (if the subject has a cardiovascular related adverse event) or at an Early Termination Visit (when the subject permanently discontinues study drug or will no longer be participating in the study)

c Expecterated sputum will be collected from subjects who are able to produce sputum

e Perform only if rolling over into Open-Label

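### Protocol 8.6.2 leaves to clinician discretion a study-drug stop that 7.2 and the synopsis make mandatory for one class of QT-prolonging drugs, and 9.1.13 omits an ECG trigger that Appendix 1 includes

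*Protocol*

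**What the plan says.** **Stopping study drug.** Protocol section 7.2, repeated in the synopsis, divides acute use of drugs known to prolong QT into two classes.

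- The first bullet begins "For drugs commonly used to treat CF patients (e.g. ciprofloxacin, levofloxacin, moxifloxacin, fluconazole, propofol, sevoflurane, ondansetron), study drug (azithromycin or placebo" and goes on to say that no stop is needed.
- The second reads "For all other drugs categorized as known to prolong QT interval, acute use is allowed but study drug" or open-label azithromycin must "be temporarily stopped during use of these medications". The word *must* is in bold.

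Section 13 lists use of a prohibited medication as a protocol violation and adds: "This includes the use of conditionally allowed medications without meeting the criteria to use these medications". The example in brackets is the temporary stop of study drug or open-label azithromycin.

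Section 8.6.2 first says that study drug should be paused for macrolides. It then says "Study drug may be temporarily discontinued at the discretion of the treating clinician during acute treatment with other medications", with these examples: "e.g., additional antibiotics or drugs believed to increase QT prolongation". It does not mention 7.2. Section 12.1 refers the reader to 8.6.2, and to no other section, for temporary discontinuation.

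**ECG at an off-schedule visit.** Section 9.1.13 says "ECG is only needed for an acute visit if the subject has a cardiovascular-related AE or will no longer be participating in the study". Footnote b of Appendix 1 requires an ECG at an unscheduled visit for a cardiovascular adverse event, and at an early termination visit "when the subject permanently discontinues study drug or will no longer be participating in the study". Section 10.6, which lists the procedures for that visit, points to footnote b.

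**The concern.** Two sections give different instructions for the same clinical situation, and the difference is between an obligation and a permission. A clinician who consults the section named for temporary discontinuation finds a discretionary rule. One who consults the concomitant-medication section finds a mandatory one. A site acting in good faith on 8.6.2 could continue study drug alongside a drug for which 7.2 requires a pause. That site would also have a violation recorded under section 13, where the Sponsor-Investigator decides whether a violation should end the subject's study treatment.

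The ECG mismatch has the same character but less at stake. Sites could differ on whether to take a tracing from someone who stops study drug for good and remains in follow-up.

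**Working it through.** No figure in the plan enters this point, so there is nothing to recompute. The check is to set the rules side by side, class by class.

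**Step 1: the stop rule during acute treatment**

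| Drug given acutely | 7.2 (7.2 and synopsis agree) | 8.6.2 | Compatible? |
|---|---|---|---|
| Macrolide antibiotic | Stop study drug | Stop study drug | Yes |
| Known to prolong QT, commonly used in CF | No need to stop | Clinician may stop | Yes |
| Known to prolong QT, all others | Stop is mandatory | Clinician may stop | **No** |
| Suspected of prolonging QT but not in the known-risk category | No rule | Clinician may stop | Yes, only 8.6.2 speaks |

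The rules collide in one row. In that row section 13 sides with 7.2, because it treats not stopping as a violation. Chronic citalopram and escitalopram have their own rule in 7.2 and fall outside 8.6.2, which concerns acute treatment.

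**Step 2: does the difference in wording remove the collision?** Section 7.2 speaks of drugs *categorized as known* to prolong QT; 8.6.2 speaks of drugs *believed* to do so. The second group is wider, but a drug known to have the effect is also believed to have it. The wider group therefore contains the mandatory-stop drugs, and 8.6.2 neither excludes them nor refers to 7.2.

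**Step 3: would a reader reach 8.6.2 without 7.2?** Section 12.1 gives 8.6.2 as its only reference on temporary discontinuation, so the protocol itself provides that route.

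**Step 4: the ECG triggers**

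| Situation at an off-schedule visit | 9.1.13 | Appendix 1, footnote b (followed by 10.6) |
|---|---|---|
| Cardiovascular adverse event | ECG | ECG |
| Subject leaves the study | ECG | ECG |
| Subject stops drug permanently, stays in the study, no cardiovascular event | Not needed | ECG |

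That is two triggers against three. The third situation is foreseen by the plan: section 12.1 asks subjects who stop treatment to attend a discontinuation visit and then encourages them to complete the remaining visits. The scheduled ECGs at Visits 1, 3 and 5 are the same in every section.

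**The case against.** The best defence of the stop rule is that specific text governs general text. Section 7.2 defines its class by reference to a named list, says *must* in bold, is repeated in the synopsis and is backed by section 13. Section 8.6.2 sits under a heading about antibiotics and can be read as a general permission for whatever 7.2 leaves open. It never says that dosing may continue where 7.2 requires a stop. On this reading the fault is a missing cross-reference. Part of this stands: someone who reads both sections would probably follow 7.2. But it relies on an order of precedence that the protocol does not state, and section 12.1 sends readers to 8.6.2 alone.

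On the ECG, the defence is stronger. Section 9.1.13 opens by deferring to the Schedule of Events, section 9 as a whole does the same, and 10.6 cites footnote b. The sentence in 9.1.13 looks like an incomplete paraphrase, which is why this part is minor.

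Sites also work from a Study Manual that is not among the documents. It may settle both points, so actual confusion at sites is inferred and not shown.

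**Conclusion.** The inconsistency in the stop rule is real and should be corrected. It is confined to acute use of known QT-prolonging drugs outside the CF-common group, and it has a practical effect only if a clinician uses the discretion in 8.6.2 not to pause. The names in 7.2 for the CF-common group are examples, so the edge of the affected class depends on how a site reads them. The documents give no basis for estimating how many of the approximately 120 subjects would be concerned.

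The ECG mismatch is secondary. It concerns only subjects who stop study drug permanently, stay in the study and have no cardiovascular adverse event.

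A reader might infer more than the documents support:

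- *That 7.2 forbids these drugs alongside the trial.* It allows their acute use, on condition that study drug is paused.
- *That everyone given a QT-prolonging drug, or everyone who stops early, is affected.* The tables above show one row of conflict in each case.
- *That the QTc endpoint is compromised.* Abnormal QTc rates are an exploratory secondary endpoint, the Visit 3 ECG remains scheduled, and subjects who stop drug are encouraged to attend it. What could be lost is the off-schedule tracing at the discontinuation visit in this small group, although it may be the one nearest to exposure.

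This is an internal inconsistency with a participant-safety aspect, not a design choice. It has no bearing on the primary endpoint, power or type I error.

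**What to change.** The sponsor and medical monitor should reconcile:

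1. Section 8.6.2 with section 7.2, the synopsis and section 13, so that one rule on pausing study drug applies to each drug class. Sections 8.6.2 and 7.2 should refer to each other, so that the pointer in 12.1 leads to the full rule.
2. The sentence in 9.1.13 with footnote b of Appendix 1 and section 10.6, so that the same ECG triggers appear in all three places.

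Which rule applies in each case is a clinical decision for them, and this review takes no position on it. The cost is a few sentences in a protocol amendment, with the IRB approval that section 17.1 requires, or a clarification memo to sites if that is judged sufficient. No change is needed to the SAP, the sample size or any planned analysis.
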